**Inclusion Criteria:**

All patients with implanted electrode arrays who are willing to participate and able to cooperate and follow research instructions will be recruited.

**Exclusion criteria** include:

IQ < 85; impairment of reading, naming, or articulation (determined by review of neuropsychology test results that are part of the patient's medical record); no cerebral pathology affecting the cortical regions from which recordings are made (determined by the neurosurgeon at the time of electrode implantation, and/or by the epileptologist who performs the clinical reading of the ECoG signals. Additionally, women who are pregnant, or who think that there is a possibility that they may be pregnant, will be excluded from participation in the study. (See "Informed Consent", below, for more detail.)

## 3. Trial Safety

Invasive monitoring EEG (a.k.a. ECoG) is indicated clinically when presurgical extracranial EEG and video EEG monitoring are inconclusive with regard to the source of seizure activity. ECoG uses subdural and depth electrodes to record electrical activity directly from the brain and clarify any inconsistencies presented by less invasive EEG results. Placement of subdural electrode grids and/or depth electrodes are determined solely on clinical grounds. There is no additional imaging (EEG, MRI, TMS) and/or ECoG electrode placement that are above and beyond the standard of care that the patient would receive if not participating in the research.

Peri-operative considerations related to the clinical procedures (i.e., not related to the research protocol) include:

- All patients admitted for invasive monitoring EEG stay in the ICU at the UW Hospital.
- Patients receive postoperative CT scans to make sure there is no bleeding.

- Patients are on antibiotics to prevent infection
- All patients monitored closely by nursing with serial neurological exams and dressing inspections to look for CSF leak.
- All patients are routinely seen by Neurology and neurosurgical staff.
- Nursing staff and EMU technologists are present 24/7 such that they immediately attend to a patient with a seizure so as to prevent any injuries. No member of the research staff will administer any clinical care. Furthermore, there is no additional clinical monitoring done solely for research purposes.
- Patients have IV seizure medication available in case seizures are too long.
- In addition to EEG there is 24 hr video surveillance as well.
- Decisions regarding resective surgery are made in case conference by consensus while patient is still in hospital.
- Acquired clinical EEG data are saved on hospital servers.

- Although all key personnel involved in data collection are required to have CPR certification, this is only a general protection given the vulnerability of the population. Because all testing will take place within the hospital's ICU, medical staff will be called immediately, per hospital procedures, should emergency clinical care be needed.

- There are two types of **specific event that would preclude a participant from continuing in the study**. The first is the subject's own volition. Participation in this study is completely voluntary, and subjects will be able to withdraw from participation at any time, for any reason. It is possible, for example, that the subject might find participation in the task unpleasant, or that the subject might find it mentally fatiguing. The second type of event could be the occurrence of one or more epileptic seizures during the time between the surgical placement of ECoG electrodes and the performance of the cognitive task. If the clinical ECoG information obtained from the seizure(s) is sufficient to inform the decisions regarding resective surgery, then there will be no clinical need for continued invasive monitoring of the patient, and research data will not be collected from that patient.

- There are no **medication-related issues** that pertain to this research project.

- **Potential risks** associated with the study are limited to potential loss of privacy, were individually identifiable health information to become available outside the study team. The following **mechanisms are in place to protect subject privacy**. *First*, the raw data will be stored on a computer server dedicated to the PI's research project, that is housed in the Department of Neurological Surgery. This computer server will be on a local area network that is physically located at the Dept. of Neurological Surgery, in a secure, restricted area, and that sits behind a password-protected firewall. *Second*, because all post-acquisition data processing will be performed in the PI's laboratory facilities in the Dept. of Psychology and the Dept. of Psychiatry, prior to transfer to the PI's lab, all data files will be renamed with a code that does not contain any identifying information (e.g., name, sex, age, date of acquisition). This code will also be used for all records of the behavioral data that are removed from the Department of Neurological Surgery. *Third*, the key linking this identifying information to the coded EEG data will be kept as a computer text file that is stored on the aforementioned computer server dedicated to the PI's research project, that is housed in the Department of Neurological Surgery. *Fourth*, a paper copy of this key will be kept in a file cabinet inside a locked room in the PI's laboratory at the Dept. of Psychology.

4. The occurrence of **Adverse Events (AEs)**, **Serious Adverse Events (SAEs)**, and **Unanticipated Problems Involving Risks to Subjects or Others (UPIRSOs)** will be reported to the PI in person, by telephone, or by email, within one day of their detection by a study team member. The PI will then submit a report in writing to the NIMH PO according to the following schedule: Death related to study participation, 5 business days; study-related SAE or UPIRSO, 10 business days; AE, with the annual progress report. Any IRB actions will be reported with the annual progress report.

## 5. Data Management, Analysis, and Quality Assurance.

- The **data sources** are ECoG signals recorded while patients perform the cognitive task, and the behavioral data associated with task performance.
  - ECoG signals from the invasive EEG electrodes are fed simultaneously to two amplifiers, one for the clinical system and one for the research system via splitter connectors.
  - To ensure that the clinical and research systems do not interfere with each other, the two systems typically use separate ground channels.
  - Because knowledge of the placement of the invasive EEG electrodes in the brain is of critical importance to both the clinician and the researcher, information about the precise location in the brain of every invasive EEG electrode is merged into to the EEG data set at an early stage of preprocessing, after the data have been collected.
  - Because the amplifier for the research data is "downstream" of the splitter connectors, it doesn't interfere with the clinical recordings in any way. Furthermore, because the research system is safety-rated and FDA-approved for invasive recordings, and does not pose any potential risk to the patient. It will consist of eight synchronized 16-channel amplifier/digitizer units that have a very low noise-floor in the high-frequency range in which the signals of interest are found, and that come with an SDK that allows them to be integrated with custom-written research software.
  - In order to capture the high-gamma signal accurately, we will acquire signals at 1200Hz sampling rate, which is considerably higher than that of the typical EEG experiment or that of many clinical monitoring systems. A built-in low-pass filter automatically prevents aliasing of signals higher than the digitizer can capture.

- **Security measures** in place to protect these data sources are described above, in Section 3, Potential Risks.

- **Quality assurance measures** will include the following:

- Careful adherence to inclusion and exclusion criteria for subject recruitment;
- Careful adherence to the data collection and analysis procedures described in the research protocol and in the NIH-approved grant application.

#### Data Analysis.

Data will be re-referenced to the average potential of all electrodes (common average reference) to avoid spatial bias due to the choice of intracranial reference electrode [5], high-pass filtered above 1.0 Hz with a symmetrical (phase true) finite impulse response (FIR) filter (~35 dB/octave roll-off).

Channels with low signal-to-noise ratio (SNR) will be identified and removed from analyses (e.g., 60 Hz line interference, electromagnetic noise from hospital equipment, amplifier saturation, and/or poor contact with cortical surface). Furthermore, a neurologist or epileptologist will identify any channels with ictal spiking activity and these channels, along with any channels over sites that were later surgically resected, will be excluded from analyses in order to reduce artifacts.

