
Data collection and processing. Clinical monitoring of the “invasive EEG” (the common clinical term for ECoG) is implemented around the clock by the surgical team of the UW Comprehensive Epilepsy Program using a 128-channel Natus NicoletOne clinical monitoring system. Signals from the invasive EEG electrodes are fed simultaneously to two amplifiers, one for the clinical system and one for the research system via splitter connectors. The research system is a 128-channel Blackrock Microsystems NeuroPort System. To ensure that the clinical and research systems do not interfere with each other, the two systems typically use separate ground channels. In the context of EEG, the “ground” electrode can be any electrode, or set of electrodes, that is part of the recording array, but that is not recording from the region of interest. It is typically an electrode that is attached to a portion of the body that is away from the brain, such as the mastoid bone of the skull, or the ear. Additionally, there is a “reference” electrode, which is located on the scalp. In a differential amplifier, the EEG signal is the result of a subtraction of the voltage between the active electrodes and the ground, and the voltage between the active electrodes and the reference. This has the effect of removing spurious environmental electrical fluctuations from the EEG. In every patient’s montage of electrodes there will be several candidate channels from which to select the ground (redundancy being an important precaution for clinical EEG), and so selecting a channel to serve as the ground for the experimental recordings will not in any way interfere with the clinical recordings, nor does it require the placement of electrodes that would not otherwise have been used for the clinical procedure. Note that, to get to this point, the patient was determined to have met inclusion and exclusion criteria prior to the surgical procedure, and so no demographic data are linked to the invasive EEG data. Knowledge of the

placement of the invasive EEG electrodes in the brain, however, is of critical importance to both the clinician and the researcher, and so information about the precise location in the brain of every invasive EEG electrode is merged into to the EEG data set at an early stage of preprocessing, after the data have been collected.

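### As written, the common average reference includes the noisy, spiking and resected-site channels that the plan later drops, so part of their signal enters every retained channel

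*Combined protocol and SAP*

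**What the plan says.** The Data Analysis section begins with re-referencing: "Data will be re-referenced to the average potential of all electrodes (common average reference"). The same sentence gives the purpose, which is to avoid depending on the choice of one intracranial reference, and adds a high-pass filter above 1.0 Hz.

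Exclusions come in the following paragraph. "Channels with low signal-to-noise ratio (SNR) will be identified and removed from analyses", with these examples: "60 Hz line interference, electromagnetic noise from hospital equipment, amplifier saturation, and/or poor contact with cortical surface". Electrodes that a clinical reader flags for ictal spikes are dropped as well, and resected sites get the same treatment: "along with any channels over sites that were later surgically resected, will be excluded from analyses in order to reduce artifacts".

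Both exclusions are from analyses. Neither is tied to the reference, and no other section says that the average is taken over retained channels.

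**The concern.** A common average reference subtracts the mean of its member channels from every channel. If a member carries large noise that the others do not share, a fraction of that noise is written, with the same waveform, into every channel that is kept. Excluding the bad channel afterwards does not take it out again.

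The measures exposed are the main ones in Statistical Considerations. Sub-study A selects electrodes by their 70-250 Hz power. Sub-study B, Stage 1, trains classifiers on high-gamma values at each electrode. Stage 2 tests above-baseline high-gamma power and interregional phase-amplitude coupling (PAC). Noise common to all electrodes raises the high-frequency floor and makes electrodes look more alike, which blurs the electrode selectivity that these steps rely on. Each sub-study needs interpretable data from only 4 patients, so one degraded recording carries weight.

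**Working it through.** The plan gives no figure on this point, so there is none to reproduce. The leak follows from the definition of the reference.

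**Inputs from the documents**
- Members of the average: all electrodes (Data Analysis).
- N, at most 128: "The research system is a 128-channel Blackrock Microsystems NeuroPort System" (Data collection and processing), and "eight synchronized 16-channel amplifier/digitizer units" in DSMP section 5, where 8 × 16 = 128. This is system capacity, not a stated count of implanted electrodes.
- Pass band: 1 Hz (high-pass filter) to 600 Hz (half the 1200 Hz sampling rate). High-gamma: 80-150 Hz (Specific Aims).

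**Assumptions, not in the documents**
- b bad channels, each with noise SD equal to k times the SD of a good channel.
- Good channels mutually independent, so that any correlation found is induced.

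**Formulas**
- Re-referenced channel: y_i = x_i − (1/N) Σ x_j. Each member contributes 1/128 = 0.78% of its amplitude at N = 128.
- Leaked SD: √b × k / N for independent noise; b × k / N for noise in phase across the bad channels.
- Induced correlation between two retained channels: about v / (1 + v), with v the leaked variance.

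**Broadband results, N = 128, independent noise**

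| Bad channels | k | Leaked SD | v | Induced correlation |
|---|---|---|---|---|
| 1 | 10 | 10/128 = 0.08 | 0.006 | 0.006 |
| 10 | 20 | √10 × 20/128 = 0.49 | 0.244 | 0.20 |
| 1 | 100 | 100/128 = 0.78 | 0.610 | 0.38 |

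Fewer electrodes raise the leak. At an assumed N of 64, each leaked SD doubles (0.16, 0.99 and 1.56).

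**High-gamma band.** Assume further that the good signal has a 1/f-squared spectrum and that the channel noise is white.
- Signal share in 80-150 Hz: (1/80 − 1/150) / (1 − 1/600) = 0.58%.
- Noise share: 70/599 = 11.7%.
- Noise-to-signal SD ratio in the band is multiplied by √(11.7/0.58), about 4.47.
- One channel at 20 SD broadband is then about 89 SD in the band and leaks 89.4/128 = 0.70 SD (v = 0.49, correlation 0.33).

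**Simulation check** (N = 128, 20,000 samples, independent good channels). Mean correlation between retained channels:

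| Bad channels | k | Independent noise | In-phase noise | Reference from retained channels only |
|---|---|---|---|---|
| 6 | 10 | 0.03 | 0.18 | −0.01 |
| 13 | 10 | 0.07 | 0.51 | −0.01 |
| 13 | 50 | 0.67 | 0.96 | −0.01 |

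The last column is the ordinary offset of any common average, about −1 divided by the number of retained channels. Leakage from excluded channels is then exactly zero.

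**The case against.** **Order is not stated.** The section uses no sequencing words, and the word all may only contrast an average with a single reference electrode. The team may intend to drop bad channels first, and the detail may sit in the cited reference or the grant application, neither of which is available here. This stands, and it limits the point to the text as written. But DSMP section 5 makes adherence to the described procedures a quality-assurance measure, and an analyst who follows this text literally would average in the bad channels.

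**Resected sites.** A reader might infer that resected-site channels must sit in the reference because they are known only after surgery. That does not follow. Processing is done after acquisition, DSMP section 3 says resection decisions are made while the patient is still in hospital, and the plan speaks of these sites in retrospect. The average can be formed once they are known. Such a channel also matters only if its signal is abnormal.

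**Line noise and saturation.** In-phase line noise gives the most striking number: ten channels at 20 SD leak 10 × 20/128 = 1.56 SD, a correlation of 0.71. That figure is broadband. The 60 Hz fundamental lies outside 8-13, 80-150 and 70-250 Hz; only harmonics such as 120 Hz, or the back-up 40-160 Hz ROC analysis, would be exposed. A channel held at saturation is flat and is largely removed by the 1 Hz high-pass, so mainly its transitions leak.

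**Bias.** A reader might infer biased contrasts or false PAC. The key comparisons (ignored against irrelevant; attended against unattended memory items) are within patient. Leaked noise unrelated to condition mainly costs sensitivity, and no effect on PAC is calculated here. Enrolling 10 patients for 4 interpretable recordings also limits the worst cases.

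**Conclusion.** The point holds as a defect in the written procedure, with medium confidence because the order of steps is inferred from the wording and sequence. The size cannot be taken from the documents. Under the assumed noise levels in the first table, the induced broadband correlation runs from about 0.006 to 0.38; the high-gamma example gives 0.33 and rests also on the assumed spectra. A few channels with modest independent noise do almost nothing. Many bad channels, very large noise, or broadband noise seen in the high-gamma band can matter.

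The main source is noisy or poorly contacted channels. The supported consequence is reduced sensitivity of the high-frequency measures, through diluted electrode selectivity and inflated between-electrode correlation. The documents do not support saying that the contrasts are biased or that the contamination certainly occurs. The change should be made before analysis because it is specific and nearly free.

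**What to change.** Replace the re-referencing sentence with:

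> Low-SNR, spiking and later-resected channels are identified and excluded first; the common average reference is then computed from the retained channels only, and the number of channels averaged is reported per patient.

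Form the average, or recompute it, once the resected sites are known.

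The cost is one sentence and a reordered preprocessing script. No retained data are lost, since the exclusions are already planned. The average uses slightly fewer channels: if ten of 128 were dropped, the SD of the mean of independent channels would move from 1/√128 = 0.088 to 1/√118 = 0.092 of a channel's SD. If the team already works this way, the change only records it.

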#### Statistical Considerations:

Sub-study A: The analyses will proceed in two stages. The first will be to determine the spatial selectivity of each ECoG electrode by calculating its response, in high-frequency (70-250 Hz) broadband power to each of the four locations stimulated during the Receptive Field Mapping task. Also of interest will be fluctuations in alpha-band power (8-13 Hz), and in phase-amplitude coupling (PAC) between alpha-band oscillations in the ECoG signal and high-frequency broadband power.

Data analysis from the Attention Task will focus on electrodes identified in the Receptive Field Mapping task to be preferentially responsive to one, or a subset, of the four critical locations. For each of these electrodes, values of alpha-band power and PAC will be analyzed as a function of attentional condition: attended (i.e., cued with 75% likelihood); ignored (i.e., cued with 25% likelihood); or irrelevant. Although a recent study has looked at alpha-band power as a function of attended vs. ignored [14], the proposed study will differ from this in two important ways. First, our critical comparison is between ignored vs. irrelevant; second, all conditions in our task will be within the same informational domain and sensory modality (i.e., visuospatial perception), whereas that of [14] spanned both (i.e., it used switches between an auditory and a motor task). Because this previous study collected 190 trials per subject [14], we believe that our design, which will collect a total of 384 trials, will be sufficiently powered to carry out the analyses of interest.

As indicated earlier in this protocol, the ECoG study that discovered and characterized the phase-encoded selection mechanism that originally motivated our decision carry out these ECoG experiments [70] made this discovery in data from four patients, with a design that yielded 20-30 trials/condition/patient; thus our design, intended to collect a minimum of 40 trials, will be adequately powered to detect effects of interest at the single-subject level. We note, however, that during his sabbatical year (spent in the lab that published [70]) the PI has observed that as many as double (or more) the final number of subjects desired for an experiment need to be recruited and to participate in it. This is due to several reasons, among them that the ECoG recordings can be contaminated with some much noise that the data are not interpretable, or because a patient's behavioral performance is too poor. Thus, for this sub-study, we plan to enroll 10 patients, with the intent of needing interpretable data from 4.

Sub-study B: The analyses will proceed in two stages. The first will be to identify stimulus-selective electrodes, the second, to test the phase-encoded selection hypothesis. That is, although the overarching motivation for this research is to test the idea that the mechanism of phase-encoded selection governs the attentional prioritization of one among multiple items held in working memory, we

will first need to determine the physiological code, carried by the ECoG signal, with which items are represented in working memory.

Stage 1. Because we do not know, *a priori*, the characteristics of the neural code underlying the representation of stimulus information in working memory, Stage 1 of the analyses will necessarily have an exploratory quality. At a general level, however, we have principled reasons for first applying MVPA to the ECoG data, and, second, as a back-up plan, applying ROC-based analyses of electrode selectivity. The rationale for starting with MVPA is twofold: first, the novel insights derived from [31-33, 60] were made possible by the application of MVPA; second, MVPA is quite simply more compatible than are univariate methods with the near-universally accepted idea that the brain represents information via distributed patterns of neural activity [e.g., 25, 29, 43]. The first step with MVPA will be to train classifiers to discriminate each stimulus with high-gamma values measured at each electrode in the array during the sample presentation epochs, then to feed data from the delay periods to the sample-trained classifiers. Although this train-on-sample-test-on-delay approach has been successful for decoding stimulus information from fMRI and EEG datasets [e.g., 17, 31, 33, 34, 36, 37, 58, 60], it does assume that the neural representation of information being held in working memory will be the same as it is when that information is being perceived and encoded. Therefore, we will also be prepared to employ a hold-one-trial-out cross validation approach, in which MVPA classifiers will be iteratively trained and tested on data from the Delaypost-cue epochs. The duration of an analysis “epoch” and, indeed, the very data that will be used to train MVPA classifiers, cannot be known until we begin working with these data. For example, with fMRI, MVPA cross validation can be performed on a TR-by-TR basis, the highest temporal resolution possible with fMRI [e.g., 17, 33, 34, 36, 37, 58]. With EEG, however, MVPA performance varies with the width of the sliding window within which spectral power is computed [31, 60], presenting a tradeoff of temporal resolution for classifier performance. Furthermore, because ECoG presents such a rich array of measures, we can’t know *a priori* whether MVPA might be most effective when applied to, e.g., broadband power [39], PAC [66], an event-related potential (ERP), or some other measure.

If we are successful, with MVPA, at decoding the identity of each of the three stimuli in the stimulus set, we will use the top 10% of electrodes contributing to the discrimination of each stimulus for Stage 2 of the analysis. (I.e., we will use the electrodes with the highest loadings in the importance map of the trained classifier corresponding to each stimulus.) Should the MVPA analyses not yield stable results, however, our back-up plan for Stage 1 will be to quantify each electrode’s selectivity for each item in the stimulus set with receiver operating characteristic (ROC)-based analyses. Such analyses have long been used to quantify the selectivity of single neurons recorded with extracellular electrodes, and a very similar approach has been used successfully in studies carried out by investigators from the ECoG consortium from which patients will be recruited for this project. For example, Parvizi and colleagues [51] indexed the selectivity of electrodes located in mid-fusiform gyrus, for faces vs. non-face stimuli, with a “signal-to-noise ratio” analysis of broadband oscillatory signals in the 40-160 Hz range. Voytek et al. [70] found that condition-specific fluctuations in the magnitude of PAC indexed selectivity of PFC electrodes for specific S-R mapping rules. Therefore, we also expect that oscillatory power in the 40-160 Hz range will be effective for deriving robust ROC estimates.

Stage 2. Having identified stimulus-selective electrodes in Stage 1 of our analyses, Stage 2 will effect the test of the phase-encoded selection hypothesis. Specifically, we will test the hypothesis that UMLs and AMIs will each be maintained in an active state, as manifested by above-baseline high-gamma power, but that the amplitude of this high-gamma power will be markedly higher for AMIs. Furthermore, this differential level of high-gamma power will be explained by the fact that the (pattern of) electrodes representing the AMI will exhibit higher interregional PAC than will the UMI. Because Voytek and colleagues [69] have shown that PAC in posterior regions tends to be anchored in the alpha band (as contrasted with a bias toward theta-paced PAC in frontal cortex), we expect that the attention-related changes in interregional PAC in ITS, mid fusiform gyrus, VO1, and/or STS, may also be concentrated in the alpha band. Assuming that we do find evidence for a phase-encoded selection mechanism in our working memory task, an important question will be to determine the source of the low-frequency oscillation clocking the predicted selection-related increase in interregional PAC. Our *a priori* working hypothesis is that this will be the “posterior alpha” that is prominent in EEG electrodes

over parietal cortex, strongly associated with visual attention (e.g., [50, 59, 67]), and widely assumed to be generated by thalamocortical circuits encompassing the caudal intraparietal sulcus.

One important point highlighted in our research plan is the fact that study [70], on which the data analysis plan of the present protocol was based, is “limited” to four patients, and to 20-30 trials/condition/patient, it nonetheless featured sufficient power to support, for example, trial-by-trial prediction of behavioral RT, and msec-level resolution of the onset of event-related phase-encoding (i.e., of phase-encoded selection).

As indicated earlier in this protocol, the ECoG study that discovered and characterized the phase-encoded selection mechanism that we will investigate in the present study [70] made this discovery in data from four patients, with a design that yielded 20-30 trials/condition/patient; thus our design, intended to collect a minimum of 40 trials, will be adequately powered to detect effects of interest at the single-subject level. As noted above, however, during his sabbatical year (spent in the lab that published [70]) the PI has observed that as many as double (or more) the final number of subjects desired for an experiment need to be recruited and to participate in it. This is due to several reasons, among them that the ECoG recordings can be contaminated with some much noise that the data are not interpretable, or because a patient’s behavioral performance is too poor. Thus, for this sub-study, we plan to enroll 10 patients, with the intent of needing interpretable data from 4.

**Data and Record Keeping:** Clinical monitoring of ECoG signals is implemented around the clock using a 192-channel Nihon-Kohden Neurofax monitoring system. Signals from the ECoG electrodes are fed simultaneously to two amplifiers, one for the clinical system and one for the research system via splitter connectors. To ensure that the clinical and research systems do not interfere with each other, the two systems typically use separate grounds. Whether research or clinical recording system, the grounding electrode is chosen to be distant from the predicted epileptic focus and from cortical areas of interest for the research. The research system will consist of eight synchronized 16-channel g.USBamp amplifier/digitizer units (g.tec, Graz, Austria). These were chosen because they are safety-rated and FDA-approved for invasive recordings, they have a very low noise-floor in the high-frequency range in which the signals of interest are found, and they come with an SDK that allows them to be integrated with custom-written research software. In order to capture the high-gamma signal accurately, we acquire signals at 1200Hz sampling rate-considerably higher than that of the typical EEG experiment or that of many clinical monitoring systems. A built-in low-pass filter automatically prevents aliasing of signals higher than the digitizer can capture. The raw data will be stored on a computer server dedicated to the PI’s research project, that is housed in the Department of Neurological Surgery. All post-acquisition data processing will be performed in the PI’s laboratory facilities in the Dept. of Psychology and the Dept. of Psychiatry. Prior to transfer to the PI’s lab, all data files will be renamed with a code that does not contain any identifying information (e.g., name, sex, age, date of acquisition). The PI’s lab manager, [name], will be responsible for the deidentification of these data, and their transfers to computer servers in the PI’s laboratory.

Once the results from data analyses have been published, the data whose analysis went into the publication will be transferred onto tape for archival storage in the PI’s laboratory, and deleted from the computer drives.

**Bibliography & References Cited:** Allows the reviewers to better understand the context of the study in light of other research available

1. Baddeley, A.D., *Working Memory*. 1986, London: Oxford University Press.
